13 STATISTICAL CONSIDERATIONS

The characteristics of patients and their disease will be described for the study as a whole and by study site using summary statistics (including means, standard deviations, quantiles) and graphical displays (e.g., boxplots) for quantitative variables and frequency distributions and proportions for qualitative data. Clinical and immune response rates will be estimated along with exact 95% confidence limits. Similarly, for each immunological parameter, summary statistics and graphical displays will be provided at baseline, before radiation, at week 5, and at week 15. Tests for normality will be used (eg Kolmogorov-Smirnov tests at alpha = 0.05); transformations (eg, logarithmic) will be used to meet the normality assumptions. The patterns of change over time for each of the immunologic parameters will be evaluated using mixed effects regression models that incorporate time as a fixed effect and subject as a random effect, and take into account different numbers of observations for each patient (missing data, [83]). Exploratory analyses will also be undertaken to describe the association of these parameters and changes in parameters with response recognizing that the numbers of subjects will be small. Additionally, the TGF β gene suppressor signature (see 9.1.1.) will be estimated for each subject and the AUC (area under the Receiver Operating Characteristic Curve) will be estimated. The sensitivity and specificity of the defined cut point will be also be provided along with 95% confidence intervals.

14.1 Endpoints

14.1.1 Primary endpoint

1. To assess safety and feasibility of combining TGF β receptor I kinase inhibitor LY2157299 and local radiotherapy
2. To determine if treatment with TGF β receptor I kinase inhibitor LY2157299 and localized RT achieves an abscopal tumor regression

14.1.2 Secondary endpoints

1. To estimate the local response rate of combining TGF β receptor I kinase inhibitor LY2157299 and local radiotherapy
2. To determine if treatment with TGF β receptor I kinase inhibitor LY2157299 and

localized RT enhances tumor-specific immunity in patients with metastatic breast cancer, and if this is associated with abscopal tumor regression.

3. To determine if treatment with TGF β receptor I kinase inhibitor LY2157299 and localized RT alters the numbers and function of T-reg cells in patients with metastatic breast cancer.

A. Analysis Populations

Efficacy analysis will be conducted on all patients who are entered into the study and received any treatment. Additional supportive efficacy analyses will be conducted for those patients who have completed week 15 visit.

B. Sample Size

i. Accrual estimates

Expected number of eligible patients will be 4 per month.

ii. Sample size justification

In this trial, a total of 28 patients with metastatic breast cancer will be accrued both at WCM and at UCLA (18 patients at WCM and 10 patients at UCLA) to treatment with radiotherapy + 300 mg/daily LY2157299 for 14 days on / 14 days off, and followed for evaluation of abscopal responses based on the immune response criteria at 15 weeks. With 28 patients enrolled in this study, we can test the null hypothesis that the abscopal response rate at 15 weeks is ≤ 0.05 versus the alternative that the response rate is 0.19 with $\alpha = 0.05$ and power of 80%. If there are 3 or fewer responses in the 28 patients, then the combination will be rejected for further study in this single stage design (calculations from PASS 2008, J. Hintze, NCSS, Kaysville, Ut). The trial is designed to allow for up to 56 patients to be enrolled to ensure that 28 patients will be evaluable at 15 weeks. Response rates will also be estimated for all enrolled patients.

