Short Title:	LY2157299 and Radiotherapy in Metastatic Breast Cancer
Clinical Phase:	Phase II
Principal Investigator:	[name], M.D.
Sample Size:	N= 28 (WCM will enroll a total of 18 patients and UCLA will enroll 10 patients)
Accrual Ceiling:	35
Study Population:	Patients must have biopsy proven metastatic breast cancer and have stable disease or progressed after at least one course of chemotherapy or hormonal therapy. This study will not enroll vulnerable population. Women > 18 years and < 90 years.
Accrual Period:	3 years
Study Design:	TGFB blockade will enhance response of irradiated tumors and improve the function of Dendritic and T cells. Patients will receive 300 mg/day of study drug administered via oral drug tablet every day for 14 days on and 14 days off (=28 day cycle). Radiation to a metastatic site will be delivered at a dose of 7.5 Gy, given consecutively on days 1-3-5.
Study Duration:	Study participation will involve 15 visits over the course of 16 weeks (approx.4 months). Patients will have an annual follow-up up to 5 years.
Study Agent/	
Intervention Description:	LY2157299 will be administered oral drug tablet: 300mg/day. Patients will receive 300 mg/day of study drug administered via oral drug tablet every day for 14 days on and 14 days off (=28 day cycle) .
Primary Objective:	1. to assess safety and feasibility of combining TGFβ receptor I kinase inhibitor LY2157299 and local radiotherapy 2. To determine if treatment with TGFB receptor I kinase inhibitor LY2157299 and localized RT achieves an abscopal tumor regression;
Secondary Objectives:	1. to estimate the local response rate of combining TGFB receptor I kinase inhibitor LY2157299 and local radiotherapy 2. To determine if treatment with TGFB receptor I kinase inhibitor LY2157299 and localized RT enhances tumor-specific immunity in

patients with metastatic breast cancer, and if this is associated with abscopal tumor regression.

3. To determine if treatment with TGFB receptor I kinase inhibitor LY2157299 and localized RT alters the numbers and function of T-reg cells in patients with metastatic breast cancer.

Endpoints:

Primary Endpoint: A. To assess safety and feasibility of combining TGF β receptor I kinase inhibitor LY2157299 and local radiotherapy
B. To determine if treatment with TGFB receptor I kinase inhibitor LY2157299 and localized RT achieves an abscopal tumor regression

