11.1 Anti-tumor Effect

11.1.1 Definitions

Patients will be evaluated by PET/CT or CT(chest/abdomen/pelvis) at baseline, week 5 and week 15. However, systemic anti-tumor response will be by PET/CT or CT(chest/abdomen/pelvis) as defined by irRC at 15 weeks (primary endpoint).

Patients who have received at least one 14 days cycle of the study drug will be followed for toxicity (lack of grade 4 toxicity— primary safety end point). Patients will receive a total of 14 doses of LY2157299 (one dose daily for 14 consecutive days), per cycle. Patients who have received any treatment will also be evaluated for abscopal response to the metastatic sites using the immunologic response criteria based on the 5 and 15 week PET/CT or CT(chest/abdomen/pelvis) scans as outlined above in Table 2.

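### The only go/no-go cut-off is set for 28 patients, but the plan does not fix which patients, or how many, the primary abscopal test counts

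*Combined protocol and SAP*

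**What the plan says.** Section 14.1.2 Part A (Analysis Populations) defines the main set: "Efficacy analysis will be conducted on all patients who are entered into the study and received any treatment". It then gives completers a secondary place: "Additional supportive efficacy analyses will be conducted for those patients who have completed week 15 visit". Section 11.1.1 is in line with the first of these: "Patients who have received any treatment will also be evaluated for abscopal response to the metastatic sites".

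Part B.ii (Sample size justification) gives the test. The null is an abscopal response rate at 15 weeks of at most 0.05, the alternative is 0.19, alpha is 0.05 and power is 80%, in a single stage. It begins "With 28 patients enrolled in this study, we can test the null hypothesis", and its decision rule is "If there are 3 or fewer responses in the 28 patients, then the combination will be rejected for further study". It then says the trial is "designed to allow for up to 56 patients to be enrolled to ensure that 28 patients will be evaluable at 15 weeks", and ends "Response rates will also be estimated for all enrolled patients".

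The Protocol Summary gives N = 28 as an enrolment total ("WCM will enroll a total of 18 patients and UCLA will enroll 10 patients"), and its Accrual Ceiling row gives 35.

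No section defines evaluable, says how a treated patient without a week-15 assessment counts in the test, or gives a cut-off for any number other than 28.

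**The concern.** The 28 is described both as the number enrolled and as the number to be evaluable out of a larger enrolment. Part A points to a test on everyone treated, which could be more than 28. Part B's closing sentence, with its word for an additional estimate in all enrolled, points to a test on 28 evaluable patients, which is the set Part A calls supportive. The two enrolment limits, 35 and 56, cannot both hold.

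This is the only go/no-go rule for the primary efficacy question in a single-arm trial. If the denominator is settled after the responses are known, an ineffective combination can be taken forward more often than the stated 5% of the time. If only evaluable patients count, those lost before week 15 leave the denominator. Section 5.7 lists progression and intolerable adverse events among the reasons for removal from treatment, so such losses may not be neutral.

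**Working it through.** **Inputs.** From section 14.1.2 B.ii: p0 = 0.05, p1 = 0.19, alpha 0.05, power 80%, n = 28, pass at 4 or more responses, up to 56 enrolled. From the Protocol Summary: ceiling 35. Sidedness is not stated, but the null and the rule are one-sided. All figures are exact binomial tails, P(X ≥ c | N, p).

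**1. The plan's own figures.**
- Error: P(X ≥ 4 | 28, 0.05) = 1 − (0.2378 + 0.3505 + 0.2490 + 0.1136) = 0.0491.
- Power: P(X ≥ 4 | 28, 0.19) = 1 − (0.0027 + 0.0180 + 0.0570 + 0.1158) = 0.8065.

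Both reproduce. 28 is also the largest N at which a cut-off of 4 keeps the error at or below 0.05, so the rule has no slack.

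**2. Cut-off of 4 carried over to all treated patients.**

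| N treated | Error at 0.05 | Power at 0.19 |
|---|---|---|
| 28 | 0.049 | 0.81 |
| 29 | 0.055 | 0.83 |
| 35 | 0.096 | 0.92 |
| 56 | 0.307 | 0.997 |

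**3. Same data, two answers.** Take 35 treated, 28 evaluable, 4 responders, all among the evaluable. On 28, p = P(X ≥ 4 | 28, 0.05) = 0.049. On 35, p = P(X ≥ 4 | 35, 0.05) = 0.096.

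**4. Test on 28 evaluable only.** Assume the 5% null is a rate among all T treated patients, and let r be the response rate in the non-evaluable. The null rate in the evaluable is then (0.05·T − r·(T − 28))/28.

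| T | r | Rate in evaluable | Chance of passing |
|---|---|---|---|
| 35 | 0.05 | 0.0500 | 0.049 |
| 35 | 0.025 | 0.0563 | 0.070 |
| 35 | 0 | 0.0625 | 0.094 |
| 56 | 0.05 | 0.0500 | 0.049 |
| 56 | 0.025 | 0.0750 | 0.154 |
| 56 | 0 | 0.1000 | 0.305 |

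The r = 0 rows are upper bounds.

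**5. Whether 35 can deliver 28 evaluable.** Enrolling 56 for 28 allows for 50% loss; a ceiling of 35 allows for 1 − 28/35 = 20%. The plan states no evaluable rate, so these are assumed rates q. P(X ≥ 28 | 35, q) is 0.98 at q = 0.9, 0.60 at 0.8, 0.13 at 0.7, 0.01 at 0.6 and 0.0003 at 0.5.

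**6. Exact cut-offs on all treated.** The smallest c with P(X ≥ c | N, 0.05) ≤ 0.05:

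| N treated | Cut-off | Power if 19% of all treated respond |
|---|---|---|
| 20–27 | 4 | 0.54–0.78 |
| 28 | 4 | 0.81 |
| 29–33 | 5 | 0.67–0.78 |
| 34 | 5 | 0.80 |
| 35 | 5 | 0.82 |
| 36–40 | 5 | 0.84–0.90 |
| 41–53 | 6 | 0.82–0.95 |
| 54–56 | 7 | 0.91–0.93 |

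If instead 19% applies only to assessed patients and the rest count as non-responders, the rate among all treated is diluted. At 20% unassessed it is 0.19 × 0.8 = 0.152, with power 0.63 at N = 28 or 35. At 50% it is 0.19 × 0.5 = 0.095, with power 0.27 at N = 28 and 0.28 at N = 56.

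**The case against.** The best counter-reading is that Part B means a test on 28 evaluable patients. The rule refers to those 28, the extra enrolment exists to obtain them, and the all-enrolled rate is an additional estimate. Part A speaks of efficacy analysis without mentioning the hypothesis test. On this reading, and if the 5% null is a rate among assessed patients, the error is 0.049 and nothing is inflated. This is a fair reading of Part B, but Part A calls that same set supportive, evaluable is undefined, and 35 still contradicts 56.

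It is also true that no section applies a cut-off of 4 to 29, 35 or 56 patients. The 0.096 and 0.307 therefore show the consequence of one reading and are not a stated rule; 56 also lies above the Protocol Summary ceiling. In the 35-patient example, the only written cut-off would pass on either denominator; the contrast comes from holding the 5% level at 35. These limits stand, and they follow from the plan giving no cut-off beyond 28.

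Section 11.1.4.4 and Table 2 require a response to be confirmed at least 4 weeks later, and the scheduled on-study scans are at weeks 5 and 15. A patient without a week-15 scan would therefore ordinarily have no confirmed response. That supports counting such patients as non-responders, but the plan does not say so and it supplies no cut-off.

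Finally, if exactly 28 are treated and all are assessed, every reading agrees. The difficulty arises with over-enrolment or loss, and the plan provides for both.

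**Conclusion.** The concern holds. The stated error and power are correct for 28 analysed patients, but the text that should fix that number contradicts itself on the analysis set and on the enrolment limit.

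The consequence depends on the reading. Keeping the cut-off at 4 for all treated patients raises the error above 5% as soon as 29 are treated, with power rising too. Testing only 28 evaluable patients leaves the error at 0.049 if the null rate holds among them. If the null is an all-treated rate and losses respond less often, the chance of passing at the null rises, at most to 0.094 with 35 treated or 0.305 with 56. Those bounds, the evaluable rates and the diluted power figures rest on assumptions the plan neither makes nor excludes.

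Because the go/no-go decision can turn on the choice of denominator, this must be fixed before results are known.

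**What to change.** 1. State that the primary test uses Part A's set, all treated patients, and that a patient without a week-15 assessment counts as a non-responder.
2. Give the cut-off by number treated: at least 4 responses for 20–28, 5 for 29–40, 6 for 41–53, and 7 for 54–56. This holds the exact error at or below 0.05 throughout.
3. Reconcile 35 and 56 to one enrolment limit, and end accrual on a rule that does not look at responses.
4. Restate power by N. It is below 80% at 20–27 and at 29–33 treated, but not at 28, 34 or 35. Show the effect of unassessed patients.
5. Keep the evaluable-only rate as supportive, with evaluable defined.

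Testing exactly 28 evaluable patients would also remove the ambiguity and keep the plan's own cut-off. It would mean rewriting Part A, and it would drop early losses from the denominator.

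The cost is SAP wording and one small table, with no extra patients. The stated power becomes less favourable at some numbers treated and when assessments are missing; the change protects the error rate and does not restore power.

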APPENDIX 1 SPECIMEN COLLECTION PROCEDURES

NOTE regarding samples for TGF- β assessment:

It is important to follow special steps to reduce the release of TGF- β into the blood sample – particularly, using a straight 20 or 21 gauge needle instead of a butterfly, minimizing tourniquet

stasis, directly drawing blood into Vacutainer tubes instead of using a manual syringe and transfer, and avoiding contact EDTA. In addition, CTAD tubes are sensitive to light, so they should be kept inside the kit boxes when not in use.

The suggested method of phlebotomy is to minimize the breakage of platelets and thus the release of TGF β from platelet granules. The order of blood tubes was designed to avoid potential cross-contamination of the plasma CTAD tube with any potential anticoagulants, EDTA and heparin, as these agents may activate platelets and/or interfere with the tests.

If the sites need to draw their standard hematology and chemistry labs before any research tests, it is recommended that:

1. Standard blood tubes containing anticoagulant be drawn first (e.g. CBC, PT/INR, and PTT) followed by collection tubes which do not contain anticoagulants (e.g. serum chemistries).
2. The biomarkers should then be drawn in the order specified below in order to adequately separate the anti-coagulant tubes from the CTAD tube.

Blood draws should be performed in the following order in order to minimize cross contamination of the TGF β plasma collection:

1. SST tube (Gold hemoguard)
2. CTAD tube (blue top)

1.2 Plasma, FROZEN (TGF β 1, VEGF)

Note: CTAD tubes are sensitive to light, so they should be kept inside the kit boxes when not in use.

- Collect blood into two 4.5 mL blue top Vacutainer® (CTAD) tubes using a 20 or 21-gauge straight needle and the following special instructions:
 - Tourniquet stasis should be minimized. **If possible, do not use a tourniquet when drawing the sample for this tube.** If a tourniquet is needed, minimize the constriction strength and try to remove it at the start of the venipuncture
 - It is recommended that blood is drawn directly into CTAD tubes in order to avoid platelet shearing/destruction. Do not use a standard syringe, manual pull, and transfer to tubes method to draw blood.
 - **A central line should not be used** for blood draws the day of infusion. In the case where it is not at all possible to draw the blood peripherally, then the central line must have been flushed with 2-5 ml of normal saline to clear any heparin
- **Invert tubes 3-4 times and immediately place in ice water bath for no more than 30 minutes**
- **Remove from bath and centrifuge whole blood at 2,500 RCF (xg) for 30 minutes at 4°C. Turn the centrifuge brake OFF.**

- **Immediately after centrifugation, pipette ~0.5 mL plasma into 7-8 cryovials, Use only the top 2/3 of the plasma volume.**
- Label the cryovials with the Patient Initials, Patient ID #, sample collection date (dd/mmm/yyyy format), sample collection time (24 hour clock) and sample type as serum for the specific biomarkers.

Immediately freeze all cryovials in the upright position at or below -70°C (-20°C is NOT acceptable) in a **non-defrosting** freezer until shipped. **Keep all samples frozen until ready to ship.**

References

1. Blöbe, G.C., W.P. Schiemann, and H.F. Lodish, *Role of transforming growth factor beta in human disease*. N Engl J Med, 2000. **342**(18): p. 1350-8.
2. Dumont, N. and C.L. Arteaga, *Transforming growth factor-beta and breast cancer: Tumor promoting effects of transforming growth factor-beta*. Breast Cancer Res, 2000. **2**(2): p. 125-32.
3. Akhurst, R.J., *TGF-beta antagonists: why suppress a tumor suppressor?* J Clin Invest, 2002. **109**(12): p. 1533-6.
4. Wakefield, L.M. and A.B. Roberts, *TGF-beta signaling: positive and negative effects on tumorigenesis*. Curr Opin Genet Dev, 2002. **12**(1): p. 22-9.
5. Dumont, N. and C.L. Arteaga, *Targeting the TGF beta signaling network in human neoplasia*. Cancer Cell, 2003. **3**(6): p. 531-6.
